5.3.2.1.5 MDS-UPDRS Part III subscale: time to worsening within 18 months

Definitions of endpoints

The participant-level endpoints will be the time from Baseline to the participant's *first* 5-point increase in MDS-UPDRS Part III subscale (or to last observed time prior to ST initiation) within the 18-month period, where the 5-point increase is confirmed at the next visit record, or ST initiated before the next visit record.

Main analytical approach

Full details on the ICE handling for this estimand can be found in Section 1.2. The main ICE will be initiation of ST, this will be handled using a "composite" strategy where initiation of ST is part of the endpoint definition. Study termination and loss to follow up related to treatment "lack of efficacy" will be handled by using non-responder imputation and be considered an event as part of the composite handling strategy. All other occurrences of study termination and loss to follow up will be right-censored, i.e., analysis only takes account of events which occurred within the observed duration.

The population level summary will be the difference in target population restricted mean event time (RMET) up to the last observed event (or last observed time prior to ST initiation) between:

- UCB0599 high dose (360mg/day) and placebo
- UCB0599 low dose (180mg/day) and placebo

In this study, the RMET can be interpreted as the average time to the *first* 5-point increase in MDS-UPDRS Part III subscale within the study period or to initiation of ST, whichever comes first. This summary was chosen as it has been shown to be robust when the proportional hazards assumption does not hold, it can be estimated even under heavy censoring, and has an easy clinical interpretation (Royston and Parmar, 2013).

The RMET can be estimated as the area under a Kaplan-Meier (KM) survival curve up to a pre-specified point in time (Royston & Parmar, 2013) or in other words, the integral of the survival

function over the study period. However, a modelling approach will need to be used here so that we can adjust for gender and age at baseline. As the main analysis for time to the *first* 5-point increase in MDS-UPDRS Part III subscale, RMET from Baseline to the last observed event time will be estimated. This will be done by fitting a generalized linear model with a linear link function for the RMET, with gender and age at baseline as covariates and treatment group as the effect of interest. This model will be fitted using the inverse probability censoring weighting (IPCW) method of estimation, this method uses Kaplan-Meier estimation to obtain weights and it has been shown that weighting in this way provides an unbiased estimate for an adjusted survival curve (Calkins, 2018). By default, this approach assumes that the right-censoring mechanism is homogeneous among all participants, which may not be a valid assumption in this study; censoring in the context of this analysis will come from both ST initiation and study termination and it is possible that both may be higher or lower in the UCB0599 arms compared to placebo. This is especially true for ST initiation, if UCB0599 shows signs of efficacy it is likely that a lower number of participants will begin taking ST in these treatment groups. To counter this potential bias, we will obtain treatment group-specific weights by applying the KM estimation method separately to each group (ie, using treatment group as a stratification variable in the model).

A summary table presenting the adjusted difference in RMET of the *first* 5-point increase in MDS-UPDRS Part III subscale between each UCB0599 treatment group and placebo and the corresponding 95% CIs will be produced, this summary will also include the model estimates of adjusted RMET for each treatment group.

To support the interpretation of these analyses, a summary table will be produced showing the number and percentage of study participants who reach this endpoint by treatment group and visit. A listing will also be produced showing date and type of event (ie, 4 options: confirmed first 5-point increase, first 5-point increase followed by ST initiation, ST initiation only, or treatment-related “lack of efficacy” study termination) for each participant, based on the FAS.

Sensitivity analyses

The RMET will be estimated for each combination of treatment group and gender as the area under the Kaplan-Meier “survival” curve up to the last observed event time (ie, without using a modelling approach). A plot of these Kaplan-Meier curves will be produced, with the RMET estimates also included in the figure. These results can be used to assess the proportional hazards assumption as well as for comparison to the results using the modelling approach. Results from the log rank test (testing the null hypothesis that there is no difference between the six survival curves) will also be displayed on this plot.

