### **9.3.1.2.2 Key Secondary Efficacy Estimand: Worsening on MDS-UPDRS Part III subscale at 18-month (“De Jure” Estimand)**

#### Participant-level endpoint

Time from Baseline to the participant’s *first* 5-point increase in MDS-UPDRS Part III subscale (or to last censored time observation due to initiation of ST) within the 18-month period.

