1.2 Intercurrent events

The tables below cover all planned efficacy analyses, except for sensitivity analyses.

The strategies/approaches for handling ICEs will be as follows:

- *Treatment Policy*: all data will be included in the analysis, regardless of whether the participant remains on the assigned investigational treatment or discontinued. This will reflect the treatment effect regardless of the ICE.
- *Hypothetical*: data will be modified to mirror its value had an ICE not happened (under some hypothetical conditions). One such hypothetical condition is that the ICE occurred completely at random. In this case, all post-ICE data are set to missing (removed) and imputed under the assumption of missing at random (MAR). This strategy can be applied to ICEs which are considered uninformative with respect to the effect of interest. As a default approach, this strategy will be applied to any occurrence of an ICE affecting the existence of measurements and maximum likelihood (ML) imputation will be used for continuous gaussian-distributed endpoints where a linear mixed effect model is used for analysis (Schafer and Graham, 2002). Alternative imputation approaches will also be considered for ICEs which are considered informative with respect to the effect of interest, under the assumption of missing not at random (MNAR), such as reference-based imputation (RBI) approaches (Carpenter, Roger & Kenward, 2013) for continuous endpoints and non-response imputation (NRI) where missing responder status is imputed as non-response for binary endpoints (Floden and Bell, 2019), as well as causal inference methods (Lasch et al., 2022). This approach will reflect the treatment effect had the ICE not occurred.
- *Composite*: ICE data will be incorporated into the endpoint being analyzed. This approach will be used for the MDS-UPDRS Part II/III time to worsening analyses; a composite endpoint of time to worsening or time to ST initiation will be used as ST initiation is considered representative of a negative outcome.

Table 1-2: Overview of handling strategies for ICEs, ICE-like protocol deviations and study termination or loss to follow-up for MDS-UPDRS estimands

		MDS-UPDRS Part I-III sum score and Part I/II/III subscales	
Estimand	Primary, key secondary and secondary	Key secondary	Secondary and supplementary
Handling ICE (ST initiation)	In the absence of ST initiation	ST initiation as part of the response	Regardless of ST initiation

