Estimates for the treatment effects of interest (see above) over the 18-month period adjusted for gender and age at Baseline with corresponding 95% CI.

To support the interpretation of these analyses, a summary table will be produced showing the number and percentage of study participants who experienced 0, 1, 2, ... and up to 13 emerging symptoms/events over 18 month by treatment group.

Supplementary Analyses:

Alternative ST initiation handling strategy

The same analysis will be repeated as above but using a “Treatment policy” handling strategy for ST initiation, i.e. the definition of the endpoint will be altered so that ST initiation will no longer be considered when determining an emerging symptom.

Alternative Part II endpoint (symptoms worsening)

Definitions of endpoints

The participant-level endpoints will be the time from Baseline to the participant’s *first* 3-point increase in MDS-UPDRS Part II subscale (or to last observed time prior to ST initiation) within the 18-month period, where the 3-point increase is confirmed at the next visit record or ST is initiated before the next visit record.

ICE Handling Strategies

Full details on the ICEs handling for this estimand can be found in [Section 1.2](#). The main ICE will be initiation of ST, this will be handled using a “composite” strategy where initiation of ST is part of the endpoint definition. Study termination and loss to follow up related to treatment “lack of efficacy” will be handled by using non-responder imputation (considered as an event). All other occurrences of study termination and loss to follow up will be right-censored, i.e., analysis only takes account of events which occurred within the observed duration.

Population Summary

The population level summary will be the difference in target population restricted mean event time (RMET) up to the last observed event (or last observed time prior to ST initiation) between:

- UCB0599 high dose (360mg/day) and placebo
- UCB0599 low dose (180mg/day) and placebo

In this study, the RMET can be interpreted as the average time to the above defined event-based endpoint.

Estimator

This analysis will use the same modelling approach as described for the MDS-UPDRS Part II subscale time to worsening analysis (see [Section 5.3.2.1.5](#) for further details).

Estimates

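### SAP 5.3.2.1.5 gives three incompatible rules for participants who start symptomatic treatment without a prior 5-point Part III increase: event before the start, event at the start, or censored

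*SAP*

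**What the plan says.** The endpoint is a key secondary estimand (SAP Table 1-1). SAP 5.3.2.1.5 defines it as time from Baseline to the first 5-point Part III increase, confirmed at the next visit or followed by ST before it, with the parenthesis "or to last observed time prior to ST initiation) within the 18-month period". A near-identical parenthesis sits in that section's population-level summary. Both recur for the 3-point Part II endpoint in SAP 5.3.2.1.7 ("or to last observed time prior to ST initiation").

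On the status of ST start, SAP 5.3.2.1.5 says "this will be handled using a 'composite' strategy where initiation of ST is part of the endpoint definition". Its event listing has a separate category, "ST initiation only, or treatment-related" study termination being the next one. The RMET is interpreted as the time to the increase "within the study period or to initiation of ST, whichever comes first". SAP 1.2, to which the section refers for full details, says "a composite endpoint of time to worsening or time to ST initiation will be used", and Table 1-2 agrees.

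Yet the paragraph on the weighting method in SAP 5.3.2.1.5 states that "censoring in the context of this analysis will come from both ST initiation and study termination". Protocol 9.3.1.2.2 writes the parenthesis as "or to last censored time observation due to initiation of ST", while naming a composite strategy under its own intercurrent-event heading.

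**The concern.** The parenthesis makes sense if ST start is a censoring event: follow-up ends at the last observation before ST. It does not fit a composite in which ST start is itself the event. Applied literally, it places an event at a time when the event had not occurred. The same ST start would also carry two dates in one report, because SAP 5.3.2.4.1 dates it at the start of ST.

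The sentence on censoring raises a larger question. The model is fitted with inverse-probability-of-censoring weights, so each record must be either an event or censored. A programmer who follows one sentence rather than another will produce a different key secondary result. Few-case reassurance is not available: the SAP's Amendment 4 rationale records that more participants than expected started ST before Month 12.

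**Working it through.** **No plan figure to reproduce.** The documents give no power or RMET figure for this endpoint.

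**1. The readings, for a participant with no prior 5-point increase and ST started on Day 118**

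| Source | Status | Time |
|---|---|---|
| Endpoint sentence plus composite handling, SAP 5.3.2.1.5 | event | last observation before Day 118 |
| RMET interpretation, SAP 5.3.2.1.5; SAP 1.2 and Table 1-2 | event | Day 118 |
| Weighting paragraph, SAP 5.3.2.1.5; Protocol 9.3.1.2.2 parenthesis | censored | last observation before Day 118 |

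**2. How early the literal date is.** Shift = ST start minus last observed time.
- *Last Part III visit.* Visits are every 60 days nominally, so the shift is 0 to 60 days, mean about 30. With the 5-day windows the largest gap is (180 + 5) - (120 - 5) = 70 days. Table 1-2 ignores missed visits for this endpoint, so one missed visit gives 120 days nominally. Day 118 becomes Day 60, which is 58 days early. ST on Day 55 gives time zero.
- *Any visit.* There are also visits on Days 10, 30, 90 and 150. The largest nominal gap is then 30 days up to Month 6 and 60 days after. Day 118 becomes Day 90 (28 days early), and Day 55 becomes Day 30.
- *Time-zero cases.* SAP 3.2 reports 10/391 = 2.6% of the PPMI patients on ST by Month 3. Applied to 150 per arm, that is 0.026 x 150 = 3.9, so about 4 at most.

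**3. Effect on RMET.** With no dropout, an arm's RMET falls by (share of ST-only events) x (mean shift). The arm difference moves by the difference between the two falls.

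Assumptions for the table, which are not document figures except the 20% and 58% (SAP 3.2): exponential ST and worsening times, independent of each other; worsening dated at the next visit; 30% worsened by Month 12 on placebo; active rates equal or 30% lower; no dropout; last Part III visit reading; horizon 18 months. Each cell gives event at ST date / event at last visit / censored at last visit, in months.

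| ST by Month 12, placebo/active | Worsening, placebo/active | Placebo RMET | Arm difference |
|---|---|---|---|
| 20% / 14% | 30% / 30% | 12.37 / 12.14 / 14.35 | 0.62 / 0.68 / 0.02 |
| 20% / 14% | 30% / 21% | 12.38 / 12.15 / 14.37 | 1.52 / 1.58 / 1.07 |
| 58% / 58% | 30% / 30% | 8.48 / 7.88 / 14.38 | -0.01 / -0.01 / -0.03 |
| 58% / 58% | 30% / 21% | 8.49 / 7.89 / 14.35 | 0.47 / 0.44 / 1.12 |
| 58% / 40.6% | 30% / 30% | 8.50 / 7.90 / 14.37 | 1.80 / 1.96 / 0.00 |
| 58% / 40.6% | 30% / 21% | 8.46 / 7.86 / 14.36 | 2.53 / 2.67 / 1.13 |

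Check on row 1: the placebo ST-only share is 0.231 and the mean shift 1.00, so the fall is 0.23 = 12.37 - 12.14. Row 4 shows why the direction is not fixed. Slower worsening leaves more active participants to reach ST first (share 0.649 against 0.612), so the falls are 0.649 x 0.97 = 0.63 and 0.612 x 0.98 = 0.60, and the difference drops by 0.03.

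**4. Part III trajectories instead of independent times.** Assumptions: slope 0.19/0.35 = 0.54 points per month (SAP 3.3), slope SD 0.5, residual SD 4, confirmed 5-point rule.
- *ST hazard independent of score.* Placebo RMET falls from 9.48 to 9.32 at 20% ST and from 6.83 to 6.39 at 58%. The arm difference goes from 1.66 to 1.72 at 58% versus 45% ST, and from 1.58 to 1.63 at 40% versus 30%. At 58% ST, placebo RMET is 6.8 as an event against 10.3 as censored.
- *ST hazard rising with observed change.* With log-hazard 0.1 or 0.2 per point, placebo ST of 20%, 40% or 58%, and an active slope 35% lower, the arm difference moves by -0.002 to -0.021.
- *Across the trajectory scenarios,* placebo RMET falls by about 0.05 to 0.45 month.

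**The case against.** The strongest reply is that early dating is not the SAP's settled rule. SAP 5.3.2.1.5 sends the reader to Section 1.2, where both the text and Table 1-2 say ST initiation, and the RMET interpretation agrees. This stands: the defect is a contradiction, not one clear wrong rule. But the parenthesis is part of the endpoint definition and is repeated in the population-level summary and in 5.3.2.1.7, so it cannot be passed over as a slip.

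The SAP also says last observed time, not last Part III visit. That stands too. The two-month and time-zero figures hold only under the Part III reading.

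A reader might infer that early dating of ST events inflates the apparent benefit, because a drug that delays ST has fewer of them. The documents do not support this. SAP 1.1 and Protocol 4.2 say that progression is directly linked to ST onset. When the simulated ST hazard follows the score, the arm difference shrinks very slightly instead of growing. The increases appear only where ST is independent of score and less frequent on active treatment.

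Finally, the study is exploratory, SAP Section 2 warns against over-interpreting p-values, and the event listing would show the date and type of each event. This limits the consequences. It does not tell the programmer which rule to apply.

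**Conclusion.** The point holds as an unreconciled definition of a key secondary endpoint that should be corrected. The SAP makes ST-only participants events before ST, events at ST start, or censored, depending on the sentence followed.

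The dating question alone is modest. Under the Part III-visit reading it lowers each arm's RMET: on placebo by about 0.05 to 0.45 month in the trajectory model and 0.23 to 0.60 in the simpler model. It moves the arm difference by -0.03 to +0.16 month over all scenarios. No direction of bias in the treatment effect should be claimed.

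The event-or-censored question is the larger one. It changed placebo RMET by about 2 months at 20% ST and about 6 months at 58% in the simpler model (3.5 months at 58% in the trajectory model), and changed the arm difference by up to 1.80 months.

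These sizes rest on assumed worsening rates, ST hazards and active-arm effects, with no dropout. The contradiction itself rests only on the text.

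**What to change.** - In SAP 5.3.2.1.5 and 5.3.2.1.7, replace the parenthesis in both the endpoint definition and the population-level summary. The endpoint is the earlier of the first confirmed 5-point (3-point) increase and the recorded date of ST initiation.
- State that an ST-only participant is an event dated at the ST start date. Keep the first-increase visit date when the increase is confirmed at the next visit or followed by ST before it.
- In the weighting paragraph of SAP 5.3.2.1.5, delete ST initiation as a source of censoring. The weights should reflect only study termination or loss to follow-up not due to lack of efficacy, and the other right-censoring causes in Table 1-2.
- Align the parenthesis in Protocol 9.3.1.2.2.

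The cost is wording and one derivation line. ST onset date and time are already collected (Protocol 6.5.3), and SAP 5.1.1 already has a rule for ST dates with a missing day.
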